5.3.2 Removal of Subjects

Subjects may withdraw or be withdrawn from the study for the following reasons:

1. At their own request or at the request of their legally acceptable representative.
2. If, in the investigator's opinion, continuation in the study would be detrimental to the subject's well-being.
3. At the specific request of the sponsor.

GRIFOLS Bioscience Industrial Group	Number	BIG-CL-PRT-000019	Version	6.0	Status	Effective	Effective Date	08-Dec-2021	Page	46 of 94
	GC2006 -A Multicenter, Randomized, Open-label, Parallel Group Pilot Study to Evaluate the Safety and Efficacy of Prolastin®-C Liquid plus Standard Medical Treatment (SMT) versus SMT alone in Hospitalized Subjects with									

Also, subjects may be withdrawn for the following reasons:

1. The subject is not able to adhere to the main protocol requirements (major protocol violations).
2. The occurrence of an AE which in the investigator's opinion requires the withdrawal of the subject from the clinical trial.
3. The occurrence of pulmonary embolism whether or not related to COVID-19
4. The subject is lost to follow-up.
5. Subject's death.
6. Any event which in the opinion of the investigator impedes the subject's participation in the study.

In all cases, the reason for withdrawal must be recorded in the study record and in the subject's records.

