Appendix 1 Schedule of Study Procedures

Study Period	Screen/ Baseline	IP	SMT and Daily Evaluations ^l										Follow-Up	Follow-Up Clinic Visit Day				
			2	3	4	5±1 ^m day	6	7	8	9	10	11-14 Daily if in hospital		15± 1 day ^m	16-28 Daily if in hospital	29 ^e ± 1 day ^m	Day 60 ± 2 days	Day 90 ± 2 days
Procedures/assessments	Study Day	1	1 st IP infusion day															
Informed consent		X																
Inclusion/exclusion criteria		X																
Demography, (including age [year of birth], gender, race, and ethnicity), disease characteristics (date of exposure, date of onset ^a)		X																
Pregnancy test ^b		X																
Ordinal Scale (at the 1 st assessment of a given day) ^c		X		X	X	X	X	X	X	X	X	X	X	X	X	X	X	
National Early Warning Score (NEWS) (Appendix 2)		X		X	X	X	X	X	X	X	X	X	X	X	X	X	X	
Clinical features key symptoms: fever, cough, shortness of breath, fatigue, myalgia etc.		X		X	X	X	X	X	X	X	X	X	X	X	X	X	X	
Vital signs (temperature, systolic and diastolic blood pressure, pulse, respiratory rate)		X	X ⁱ	X	X	X	X	X	X ⁱ	X	X	X	X	X	X	X	X	
Weight		X																
Record result of historical SARS-CoV-2 PCR (qualitative RT-PCR) or NAT or other commercial or public health assay approved by regulatory authorities as a diagnostic test for COVID-19 in any specimen during the current hospital admission OR 96 hours prior to the hospital admission date and prior to randomization (the SARS-CoV-2 test results must be performed by a hospital laboratory and the documentation available) (eligibility criterion)		X																

CONFIDENTIAL

GRIFOLS	Number	BIG-CL-PRT-00019	Version	6.0	Status	Effective	08-Dec-2021
	GC2006 -A Multicenter, Randomized, Open-label, Parallel Group Pilot Study to Evaluate the Safety and Efficacy of Prolastin®-C Liquid plus Standard Medical Treatment (SMT) versus						
Bioscience Industrial Group							81 of 94

Study Period	Screen/ Baseline	IP	SMT and Daily Evaluations^l									Follow-Up	Follow-Up Clinic Visit Day				
			2	3	4	5±1 ^m day	6	7	8	9	10		15± 1 day ^m	16-28 Daily if in hospital	29 ^e ± 1 day ^m	Day 60 ± 2 days	Day 90 ± 2 days
Study Day	1	1st IP infusion day															
Procedures/assessments																	
Record any supplemental oxygen administration (type, %, flow start/end date/time)	X		X	X	X	X	X	X	X	X	X	X	X	X	X		
If subject requires mechanical ventilation post randomization: Record any mechanical ventilation (start/end date/time)			X	X	X	X	X	X	X	X	X	X	X	X	X		

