- i. During study infusions on Day 1 and Day 8 vital signs will be measured immediately before the start of infusion, after the first 5 minutes of infusion, and subsequently at 5-10-minute intervals during infusion until the end of infusion. Vital signs will also be measured 2 hours after the end of study infusion.
- j. Day 8 AAT measurement for activity and antigen is only required if subject is in hospital.
- k. If the patient has been discharged from the hospital at the time of the Day 8 blinded Liquid Alpha₁-PI (Human) or Placebo infusion, the 2nd infusion is not mandatory, and is at the discretion of the Principal Investigator and subject
- l. Only applicable if subject remains hospitalized, except for Day 5 when all assessments are mandatory for all subjects.
- m. Mandatory even if subject has been discharged from hospital

Note: For assessment for early withdrawal see Section [5.3.4](#).

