Approximately 100 subjects (who meet the inclusion/exclusion criteria specified in Protocol Sections 5.1 & 5.2) will be randomized in a 1:1 [Liquid Alpha1-PI (Human) plus SMT : Placebo plus SMT] ratio with an interim analysis after 50 subjects (approximately 25 per group). There will be no interruption in study conduct during interim analysis as this simply represents sponsor safety due diligence during the COVID-19 pandemic. An interim futility analysis will be conducted to assess whether the trial will be terminated due to lack of efficacy (futility) based on all available data assessable for the primary endpoint and key secondary efficacy endpoints.

All subjects will be followed daily through Day 10 (note: for Day 6 through Day 10, this stipulation is for as long as subjects are hospitalized). After Day 6, if subjects are discharged from the hospital, evaluations at Day 15 and 29 are required. Subjects remaining hospitalized will be followed daily through Day 29. Phone Checks will occur at Day 60 and Day 90 for vital status (living or deceased), any hospital re-admissions or serious/non-serious AEs after the Day 29 Final Clinic Visit. See Appendix A for the Schedule of Events.

Clinical trial finalization will coincide with the last study visit of the last subject enrolled in the clinical trial. For an individual subject, end of study for the purposes of determining disposition and successful study completion is the Day 29/Final Clinic Visit performed at the scheduled on-study timeframe.

An overview of the study design is presented below:

IV = intravenous; SMT = standard medical treatment

\*Note: If the subject has been discharged from the hospital at the time of the Day 8 blinded Liquid Alpha-1 PI infusion, the 2nd infusion is not mandatory, and is at the discretion of the Principal Investigator and subject

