## 4. GENERAL CONSIDERATIONS FOR DATA ANALYSIS

Unless otherwise specified, continuous variables will be summarized using descriptive statistics

(n, mean, standard deviation, median, minimum, and maximum). Categorical variables will be summarized showing the number and percentage of subjects within each category.

Summary results will be provided for each treatment group. All tabulations will be based on pooled data across centers.

All statistical tests will be two-sided and tested at the 5% level of significance.

Analyses will be performed using SAS for Windows statistical software, version 9.4 or higher (SAS, Cary, NC), except where other software may be deemed more appropriate. In the event that other software is used to perform some analyses, the details will be provided in the Clinical Study Report.

██████████ will perform all efficacy and safety analyses described in this SAP and Grifols will review them.

Subject data will be listed, sorted by treatment group and subject number. When applicable, listings will be additionally sorted by visit and assessment date/time.

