#### **4.3 Assessment Windows**

Data will be summarized by nominal study visit recorded in the database.

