## **6.2 Secondary Efficacy Endpoints and Analyses**

### **Assessment of clinical severity**

The NEWS will be calculated based on 7 clinical parameters and recorded on the eCRF. The

absolute value and change from baseline in the total score from Day 1 through Day 29 will be summarized by treatment group and visit using descriptive statistics.

Change in NEWS total score through Day 29 will be evaluated by fitting a linear mixed-effects model for repeated measures (MMRM). The model will include change from baseline in NEWS total score as the repeated dependent variable; treatment (as a class variable), visit (as a class variable), and treatment-by-visit interaction as fixed effects; baseline NEWS total score, age and gender as covariates; and measures within subject at each visit as a repeated measure. An unstructured covariance matrix will be used to model the within-subject error. If the fit of the unstructured covariance structure fails to converge, a compound symmetry covariance structure will be used. Parameters will be estimated using restricted maximum likelihood with the Kenward-Roger method for calculating the denominator degrees of freedom. Data collected starting at the Day 2 visit and up to the Day 29 visit will be included in this analysis. Missing data will not be imputed. From this model, the least-squares (LS) means and 95% CIs for each treatment group, the treatment difference in the LS means, the 95% CI for the difference, and the associated p-value will be reported on Days 15 and 29, as well as for the average across all post-baseline visits.

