### **Ordinal scales**

- a) The absolute value and change from baseline in the Ordinal scale from Day 1 through Day 29 will be summarized by treatment group and visit using descriptive statistics.

Mean change in Ordinal scales through Day 29 will be evaluated by fitting a linear MMRM similar to the one described above for “assessment of clinical severity.”

- b) The proportion of subjects in each severity category of the 7-point Ordinal scale at Day 15 and Day 29 will be tabulated. The difference in severity category distribution between treatment groups at Day 15 and Day 29 will be examined using proportional-odds cumulative logit model. The cumulative logits model will compare lower ordinal scales to higher ones, or equivalently, less favorable outcomes to more favorable ones. The model may be adjusted for baseline characteristics such as age and gender if appropriate. The estimated odds ratio and 95% CI will be presented. Graphical illustrations of the fitted model will also be presented for Day 15 and Day 29.

The proportional odds assumption will be tested using a score test at the two-sided alpha level of 0.05. If the proportional odds assumption is not satisfied, given the anti-conservative nature of the score test, the proportional odds model will still be used for the analysis, and the results will be presented along with the score test p-value to help put these results in context. If the proportion odds assumption is rejected or if the proportional odds model fails to converge, a sensitivity or alternative analysis using a non-parametric Wilcoxon Rank Sum test will be performed. The p-value from Wilcoxon Rank Sum test, as well as the Hodges-Lehmann estimate of the treatment difference and the corresponding

95% CI will be provided.

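### The SAP gives no rule for scoring death or discharge on the ordinal scale on days without a visit, so the ordinal MMRM omits deaths and most discharged time

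*SAP*

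**What the plan says.** **Scale.** SAP 2.2.2 defines seven categories. Category 1 is death, 2 to 5 are in-hospital states, and 6 and 7 are out of hospital.

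**Collection.** Protocol Appendix 1 has the scale scored at the first "assessment of a given day". Footnote l says of the daily evaluations: "Only applicable if subject remains hospitalized, except for Day 5 when all assessments are mandatory for all subjects". Footnote m makes Days 5, 15 and 29 mandatory after discharge. The running text (Protocol 4.2, SAP 3.1) starts the hospital-only limit at Day 6. Protocol 5.3.2 lists "Subject's death" among the reasons for withdrawal.

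**Analysis (a).** SAP 6.2, Ordinal scales, gives summaries by visit and then: "Mean change in Ordinal scales through Day 29 will be evaluated by fitting a linear MMRM similar to the one described above" for clinical severity. That NEWS model takes Day 2 to Day 29, states "Missing data will not be imputed", and reports Day 15, Day 29 and the average over all post-baseline visits. SAP 4.3 adds: "Data will be summarized by nominal study visit recorded in the database".

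**Analysis (b).** All seven categories are tabulated at Days 15 and 29 and compared by a proportional-odds model, with a Wilcoxon test as the alternative or sensitivity analysis. All efficacy analyses use the ITT population.

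**Rules for death.** SAP 6.2 states how deaths are handled for duration of hospitalization, ICU stay, oxygen use and mechanical ventilation. It states nothing for the ordinal scale. SAP 4.4 promises worst-case imputation for binary and selected continuous endpoints and leaves the details to Section 6, which has none for this scale.

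**The concern.** NEWS does not exist after death, so a model of NEWS without imputation is at least coherent. The ordinal scale was built so that death and discharge have values. Apart from 6 versus 7, a subject's category on any day follows from dates already collected. Taking over the NEWS rule treats those known values as missing, and they are missing because of the outcome. A model that assumes missing at random then in effect predicts living, in-hospital scores for subjects who are dead or at home.

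At stake are the ordinal secondary endpoints. They are also among the outcomes listed for the futility review in SAP 8.2. With no written rule, two competent programmers could produce different answers, possibly of opposite sign, and the choice might be made after unblinding.

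**Working it through.** The SAP gives no power, effect size, mortality or discharge rate (Section 9), so there is no planned figure to reproduce. From the documents: "All statistical tests will be two-sided and tested at the 5% level of significance", and "Approximately 100 subjects (who meet the inclusion/exclusion criteria specified in Protocol Sections 5.1 & 5.2) will be randomized in a 1:1" ratio, so about 50 per arm. Every rate below is an assumption.

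**1. Days on which only in-hospital subjects are scored.** Days 2 to 29 are 28 days.
- Footnote l: all living subjects are scored on Days 5, 15 and 29. 28 − 3 = 25 days are hospital-only (25/28 = 89%).
- Running text: Days 2 to 4 also cover everyone. 28 − 6 = 22 days (22/28 = 79%).

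**2. True state against recorded score.**

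| State | Category | Days 5, 15, 29 | Other days |
|---|---|---|---|
| In hospital | 2-5 | recorded | recorded |
| Discharged alive | 6 or 7 | recorded | not recorded |
| Dead | 1 | no visit | no visit |

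**3. Day 29 means by hand.** Let d be the proportion dead and m the survivors' mean. With deaths scored 1 the mean is (1 − d)m + d; with deaths left out it is m. Assume survivors fall in categories 2 to 7 with probabilities 0.03, 0.04, 0.06, 0.07, 0.35, 0.45. Then m = 0.06 + 0.12 + 0.24 + 0.35 + 2.10 + 3.15 = 6.02.
- *Same survivors in both arms, deaths 20% placebo and 5% active.* The difference with deaths scored is (0.20 − 0.05)(6.02 − 1) = 0.75. With deaths left out it is 0.
- *Deaths 20% and 10%, the 10 prevented points surviving in category 3.* Scored: placebo 0.80 × 6.02 + 0.20 = 5.02; active 0.80 × 6.02 + 0.10 × 3 + 0.10 = 5.22; difference +0.20. Left out: placebo 6.02; active (0.80 × 6.02 + 0.10 × 3)/0.90 = 5.68; difference −0.34.

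The reversal does not depend on category 3. It occurs in these raw means whenever the rescued subjects average above 1 and below 6.02.

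**4. Day 29 rank test.** Same survivor distribution in both arms, 50 per arm, two-sided 0.05 Wilcoxon, 4,000 simulated trials per row.

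| Deaths, placebo/active | Rejection, deaths = 1 | Rejection, deaths left out |
|---|---|---|
| 10% / 5% | 7% | 4% |
| 15% / 5% | 16% | 5% |
| 20% / 5% | 27% | 5% |
| 30% / 10% | 45% | 5% |

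**5. MMRM over Days 2-29.** One simulated data set per scenario, 700 per arm, compound-symmetry model adjusted for baseline.
- Baseline category 3, 4 or 5 with probability 0.15, 0.70, 0.15.
- Daily death probability 0.008, multiplied by 4, 2, 0.7, 0.2 in categories 2 to 5.
- Daily discharge probability 0.08, multiplied by 0.05, 0.3, 1, 2.2 in categories 2 to 5.
- Otherwise a 6% chance of worsening and a 12% chance of improving by one category.
- Discharged subjects stay at 6 or 7.

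Placebo then has 8.3% deaths by Day 29 and 55.6% discharged by Day 10. Entries are active minus placebo, positive meaning better: full data (death = 1, discharged = 6/7) → MMRM on recorded visits under footnote l.

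| Effect of active | Average Days 2-29 | Day 15 | Day 29 |
|---|---|---|---|
| Death hazard halved | +0.08 → −0.05 | +0.11 → −0.06 | +0.15 → −0.06 |
| Discharge hazard × 1.5 | +0.18 → −0.03 | +0.26 → +0.24 | +0.12 → +0.09 |
| Both | +0.33 → 0.00 | +0.39 → +0.21 | +0.37 → +0.13 |

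Only 32% to 41% of subject-days are recorded. Simulation error was not quantified, so I read the small negative values as no effect or slight apparent harm.

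**The case against.** A reader might infer that the SAP as written drops deaths from all ordinal analyses. The documents do not say so. Analysis (b) tabulates every category, death is one of them, the population is ITT, and death is recorded on the All Visits eCRF page (SAP 6.1). The no-imputation sentence belongs to the NEWS model and is not applied to the table or the proportional-odds model. Counting deaths there is the natural reading. This stands: for (b) the fault is only that the rule is unwritten.

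A reader might also infer that the comparison is confined to in-hospital subjects and that faster discharge cannot show. That is too strong. Discharged subjects are scored on Days 5, 15 and 29, which include both days with single-day contrasts, and the simulated discharge effect largely survives there (+0.24 of +0.26; +0.09 of +0.12). The MMRM also uses each subject's earlier data. That does not rescue it, because missing at random is implausible here.

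Deaths and discharge are captured elsewhere as well: in the primary endpoint, time to clinical progression, time to discharge and the durations. Futility rests on conditional power for the primary outcome plus an unspecified look at the secondaries, so the ordinal scale has no defined deciding role. The endpoint is secondary, with no multiplicity adjustment, in an exploratory study. All of this lowers the severity; none of it supplies the missing rule.

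**Conclusion.** The gap is real and should be fixed, but it is not critical. For the daily summaries and the all-visit MMRM average, following the text literally omits deaths and most discharged time, with scores collected only in hospital on 22 to 25 of 28 days. For the Day 15 and Day 29 MMRM contrasts it omits earlier deaths but keeps discharged subjects. For the Day 15/29 table and proportional-odds model the handling of deaths is open, with counting them the likelier intention.

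The size rests wholly on assumed rates. Under them a benefit can shrink to null (+0.33 to 0.00 for the average) or change sign (+0.20 to −0.34 in the Day 29 means). At low mortality the loss in the rank test is small (7% against 4% rejection at 10% versus 5% deaths). The point about scoring at the first assessment affects only the day of death.

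**What to change.** In SAP 6.2, Ordinal scales, state:

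- **Death.** The score is 1 from the date of death through Day 29, including nominal Days 15 and 29, and it overrides any earlier score that day. This applies to the tables, the proportional-odds model, the Wilcoxon test and the MMRM.
- **Discharge.** Either limit the ordinal MMRM to Days 5, 15 and 29, when all living subjects are assessed, or score 6 (or the last recorded 6 or 7) from discharge until the next assessment or re-admission.
- **Living subjects with no Day 15 or Day 29 score.** Say how they are handled.

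The cost is a paragraph and a variable derived from death and discharge dates already collected. If scores are filled in between visits, 6 versus 7 is approximate and the constant values can overstate precision. Limiting the MMRM to three days avoids both. It also cuts the unstructured covariance from 28 × 29/2 = 406 parameters, for about 100 subjects, to 3 × 4/2 = 6.

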## 3.2 Treatment

### 3.2.1 Randomization Scheme and Treatment Arm Assignment

Subjects will be randomized 1:1 to receive either combination treatment with Liquid Alpha1-PI (Human) plus SMT or placebo plus SMT.

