### **Duration of Hospitalization**

The duration (number of days) of hospitalization from Day 1 through Day 29 will be calculated based on hospital admission and discharge dates recorded on the eCRF. Number of days in the hospital will be compared between treatment groups using an ANOVA model, including number of days in the hospital as a dependent variable and treatment group as a fixed effect. From this model, the LS means and 95% CIs for each treatment group, the treatment difference in the LS means, the 95% CI for the difference, and the associated p-value will be presented. If appropriate, an ANCOVA model may instead be used to additionally adjust for baseline characteristics such as age and gender.

Subjects who died while in the hospital will be assigned as in the hospital for the number of days remaining from the day of death to Day 29 for the analysis. Subjects who were in the hospital at

study completion will be assigned a hospitalization end date equals to the date of completion for the purpose of deriving the duration of hospitalization.

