## 9. SAMPLE SIZE AND POWER CALCULATIONS

Because of the urgency and lack of previous prospective COVID-19 data, sample size estimation remains incompletely defined; however, the size of this pilot study is commensurate with other Phase 2 investigations ongoing during the COVID-19 pandemic. Approximately 100 subjects are allowed to be randomized as part of a humanitarian effort against COVID-19.

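### The SAP leaves covariate adjustment optional in the Day 15 and Day 29 proportional-odds models and the four duration analyses, and does not name baseline ordinal category

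*SAP*

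**What the plan says.** **Proportional-odds models.** SAP 6.2, Ordinal scales, part (b), compares the category distributions at Day 15 and Day 29 with a cumulative logit model. On covariates it says only: "The model may be adjusted for baseline characteristics such as age and gender if appropriate".

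**Duration analyses.** Each of the four starts from an ANOVA with treatment as the only effect. For hospitalization the SAP adds: "If appropriate, an ANCOVA model may instead be used to additionally adjust for baseline characteristics such as age and gender". The sections on ICU stay, oxygen use and mechanical ventilation say the same.

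**Contrast within the section.** The repeated-measures model for change in NEWS has prespecified terms, including "baseline NEWS total score, age and gender as covariates". Part (a) of Ordinal scales analyses mean change with a model described as similar to that one. By analogy it contains the baseline ordinal score, age and gender.

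**What is collected.** Protocol 7.2.2 and Appendix 1 require the ordinal scale at Screening/Baseline, before randomization.

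**Where the choice was to be settled.** Protocol 9.1 allows ANCOVA or ANOVA depending on whether covariates are used, and leaves the detailed choice of method to the SAP. SAP 8.2 applies the methods of sections 6.1 and 6.2 to the futility analysis and plans no sensitivity analyses there.

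**The concern.** Six secondary comparisons (two ordinal, four duration) each have two admissible main models. Nothing defines when adjustment is appropriate, who decides, or at what point. The protocol passes the decision to the SAP, and the SAP leaves it open.

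The covariates offered as examples are age and gender. The baseline value of the scale itself is not mentioned in these analyses, although the same section fixes the baseline score for NEWS. SAP 3.2.1 and Protocol 4.3.2 name no stratification factor, so adjustment in the analysis is the only stated means of using baseline severity.

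Two things are at stake. One is some power or precision available at no cost in data. The other is a single, predictable version of each result, both in the final report and in the unblinded futility review, where secondary outcomes may contribute to a decision to stop.

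**Working it through.** **Inputs from the documents**
- Test level: "All statistical tests will be two-sided and tested at the 5% level of significance" (SAP 4).
- Size: "Approximately 100 subjects are allowed to be randomized as part of a humanitarian effort against COVID-19" (SAP 9). Allocation is 1:1 (SAP 3.2.1), so about 50 per arm.
- No power, effect size, SD or dropout is given; SAP 9 says that "sample size estimation remains incompletely defined". There is therefore no stated figure to reproduce.
- Range of the covariate: inclusion criterion 1 (hospitalized) rules out categories 6 and 7. Exclusion criterion 1 (invasive ventilation or ICU) rules out category 2. Baseline is confined to categories 3, 4 and 5.

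The baseline mix and its link to outcome are not in the documents. Both are assumed below and shown as ranges.

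**Duration analyses.** Let r be the correlation between baseline category and duration, and d the standardized difference. Adjustment multiplies the residual variance by 1 − r², so:
- power = Φ( d√(50/2)/√(1 − r²) − 1.96 ), ignoring the small loss of degrees of freedom;
- CI width ratio = √(1 − r²);
- equivalent total N = 100/(1 − r²).

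With d = 0.56 assumed and no adjustment: Φ(0.56 × 5 − 1.96) = Φ(0.84) = 80.0%.

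| r | Power | CI width ratio | Equivalent N |
|---|---|---|---|
| 0 | 80.0% | 1.000 | 100 |
| 0.1 | 80.3% | 0.995 | 101 |
| 0.2 | 81.5% | 0.980 | 104 |
| 0.3 | 83.5% | 0.954 | 110 |
| 0.4 | 86.3% | 0.917 | 119 |
| 0.5 | 89.9% | 0.866 | 133 |

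The gain is 0.3 to 9.9 points over r = 0.1 to 0.5. At smaller assumed effects the top of the range is slightly higher: for r = 0.5, 51.6% to 63.7% at d = 0.4, and 70.5% to 82.3% at d = 0.5.

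**Proportional-odds model.** This was simulated with 50 per arm, 3,000 trials per scenario and a Wald test at two-sided 0.05, with and without baseline category as a linear term (age and gender not included). Assumptions:
- Day 29 probabilities for categories 1 to 7 in a control subject starting in category 4: 0.08, 0.04, 0.03, 0.05, 0.05, 0.30, 0.45.
- Treatment log-OR 0.98.
- Baseline log-OR per category from 0 to 1.5.
- Three baseline mixes over categories 3/4/5.

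Power, unadjusted to adjusted:

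| Baseline log-OR | Mix 10/80/10 | Mix 25/60/15 | Mix 35/40/25 |
|---|---|---|---|
| 0 | 67.9 to 67.6% | 67.9 to 68.0% | 67.9 to 67.8% |
| 0.5 | 67.5 to 67.8% | 67.6 to 68.7% | 67.0 to 68.4% |
| 1.0 | 64.9 to 67.3% | 63.3 to 68.1% | 60.9 to 66.7% |
| 1.5 | 62.7 to 66.8% | 58.0 to 67.1% | 53.2 to 65.5% |

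The gains are 0.3 to 1.4 points at 0.5, 2.4 to 5.8 at 1.0, and 4.1 to 12.3 at 1.5. With no prognostic effect the change is −0.3 to +0.1 points.

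**Source of the gain.** At log-OR 1.0 with the 25/60/15 mix, the mean estimated treatment log-OR moves from 0.913 to 0.993, while the mean SE rises from 0.397 to 0.411. The ratio goes from 0.913/0.397 = 2.30 to 0.993/0.411 = 2.42. The adjusted odds ratio is conditional on baseline and lies further from 1; the SE does not shrink.

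**Type I error.** With no treatment effect and baseline log-OR 1.0, under the first two mixes, the adjusted test rejected in 5.9% and 5.2% of trials and the unadjusted test in 5.0% and 4.9%. The Monte Carlo SE is √(0.05 × 0.95/3000) = 0.4 points. A small part of the power gain may therefore be mild anti-conservatism.

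**The case against.** The other side has several fair points.

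- **Importance.** These are secondary endpoints in an exploratory study with no power target and no multiplicity adjustment, and the primary analysis is untouched. A few points of power on a secondary test is partly an efficiency preference. This stands and limits the weight of the point.
- **Size.** No document says how prognostic baseline category is. If most subjects start in category 4, which the oxygenation criteria may encourage, the gain is at the low end. This stands.
- **Model burden.** Seven outcome levels need six intercepts; with four terms that makes ten parameters in about 100 subjects. The SAP already provides a Wilcoxon test if the model fails to converge. This argues for a linear baseline term and for keeping the fallback, but not for leaving the choice open.
- **ICU and ventilation days.** The SAP itself expects that very few subjects may have any, so a gain from linear ANCOVA there is the least certain.

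A reader might also infer more than the text supports:

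- **That the model will be chosen after unblinding.** The SAP does not say so; the timing is unspecified.
- **That baseline severity is excluded or ignored for this scale.** The SAP's examples are open-ended, so baseline category is unnamed but permitted, and the mean-change model by analogy already adjusts for it.
- **That adjustment makes the odds ratio more precise.** It does not. A precision gain in the literal sense applies only to the linear duration models.

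**Conclusion.** The point holds at modest importance. Adjustment is optional and undefined in six secondary analyses, and baseline ordinal category is not named in them although it is collected before randomization. The SAP takes a firmer line for NEWS and, by analogy, for ordinal mean change.

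At 50 per arm, and under the assumed outcome distribution, effect sizes and baseline mixes, fixing baseline category is worth:
- for the proportional-odds models, about 0 to 2 power points if weakly prognostic (log-OR 0.5 per category), 2 to 6 at 1.0, and 4 to 12 at 1.5, with a conditional odds ratio as the estimand;
- for the durations, about 0 to 10 power points at d = 0.56 and intervals up to 13% narrower for r = 0.1 to 0.5.

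The direction is well supported, but the size within these ranges cannot be settled from the documents. The open choice of model is a defect whatever the size of the gain, because the futility review uses the same methods without a stated main version.

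**What to change.** Amend SAP 6.2 before any unblinded look:

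1. In Ordinal scales part (b), make treatment, baseline ordinal category (linear, to limit sparse cells), age and gender fixed terms of the main Day 15 and Day 29 models. State that the odds ratio is conditional on these covariates.
2. For the four durations, replace the default ANOVA with a prespecified ANCOVA using the same baseline covariates.
3. Delete *may* and *if appropriate* from the covariate sentences.
4. In the final analysis, report the unadjusted models as sensitivity analyses, and keep the Wilcoxon tests where the SAP already has them (ordinal scale, ICU days, ventilation days).
5. State in SAP 8.2 that the futility review uses the adjusted main models.

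The cost is SAP wording and minor programming. No new data are needed, and in the scenarios run with a non-prognostic baseline category power was essentially unchanged (67.9% unadjusted against 67.6 to 68.0% adjusted).
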